STUDY PROTOCOL

Title: Predicting Mortality in Patients With Return of Spontaneous Circulation After Cardiac Arrest

ClinicalTrials.gov Identifier: NCT07020091

Document Date: April 16, 2026

Study Design

This study is a retrospective observational cohort study conducted in a tertiary adult intensive care unit.

Study Population

Adult patients (≥ 18 years) who achieved return of spontaneous circulation (ROSC) after cardiac arrest and were admitted to the intensive care unit (ICU) between January 1, 2024 and May 31, 2025 were included. Patients were retrospectively identified from electronic medical records.

Data Collection

Baseline demographic, clinical, laboratory, and resuscitation-related variables were collected from hospital electronic systems. Data recorded within the first 24 hours of ICU admission were included in the analysis.

Outcome Measures

The primary outcome was 30-day all-cause mortality after ICU admission. Secondary outcomes included in-hospital mortality and 6-month all-cause mortality.

Statistical Analysis Plan

Continuous variables were assessed for normality using the Shapiro–Wilk test and presented as mean \pm standard deviation or median (interquartile range), as appropriate. Categorical variables were expressed as counts and percentages.

Comparisons between groups were performed using Student’s t-test or Mann–Whitney U test for continuous variables, and chi-square or Fisher’s exact test for categorical variables.

Multivariable logistic regression analysis was used to identify independent predictors of mortality. Variables with clinical relevance or statistical significance in univariable analysis were included in the model.

Receiver operating characteristic (ROC) curve analysis was performed to evaluate the discriminative performance of severity scores. The area under the curve (AUC) and 95% confidence intervals were calculated.

A p-value < 0.05 was considered statistically significant. Statistical analyses were performed using SPSS software (IBM Corp., Armonk, NY, USA).

Ethical Considerations

The study was approved by the local ethics committee, and the requirement for informed consent was waived due to the retrospective design of the study.

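### Student's t-test is planned with no provision for unequal variances between outcome groups of probably unequal size, so it can miss its 5% level in either direction

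*Combined protocol and SAP*

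**What the plan says.** All of the relevant text is in the Statistical Analysis Plan section of the combined protocol and SAP.

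- Normality: "Continuous variables were assessed for normality using the Shapiro–Wilk test". The same sentence ties this to presentation as mean and SD or as median and interquartile range. That it also chooses the test is implied, not written.
- Tests: "Comparisons between groups were performed using Student’s t-test or Mann–Whitney U test for continuous variables". Neither a Welch version nor a check of equal variances is mentioned.
- Threshold: "A p-value < 0.05 was considered statistically significant".
- Model entry: "Variables with clinical relevance or statistical significance in univariable analysis were included in the model".

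The groups are not defined. The Outcome Measures section says "The primary outcome was 30-day all-cause mortality after ICU admission", so survivors against non-survivors at 30 days is the natural reading. No sample size, expected mortality or SD is given anywhere.

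**The concern.** Student's t-test pools the two variances. When the groups differ in size, the pooled estimate is dominated by the larger group. If the smaller group has the wider spread, the standard error is too small and the test rejects too often. If the larger group has the wider spread, the test rejects too rarely.

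Groups formed by survival are not balanced by design, so the protection that equal sizes would give cannot be relied on. A normality test does not fill the gap, because two normal samples can have quite different SDs.

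At stake is the meaning of the p-values in the group comparisons, which are judged against 5%. Possibly at stake too is the set of variables offered to the logistic model, if these comparisons are what the plan means by univariable analysis.

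**Working it through.** **Inputs.** From the plan: a threshold of 0.05, taken as two-sided because sidedness is not stated. Assumed, because the plan gives no figures: 50 survivors and 100 deaths, with 40 and 110 as a more uneven case; SD ratios from 1 to 2 in either direction; normal data with equal means. The plan has no sample size or power figure to reproduce; the nominal 5% is the only figure to test.

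**Formula.** Let survivors have n₁ and s₁, and deaths n₂ and s₂. In large samples, the variance of the mean difference that Student's test assumes is

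V(assumed) = s₁²/n₂ + s₂²/n₁,

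while the true variance is

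V(true) = s₁²/n₁ + s₂²/n₂.

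The true level is 2 × [1 − Φ(1.96 × √(V(assumed)/V(true)))]. The two variances are equal whenever n₁ = n₂ or s₁ = s₂, so the level is lost only if both the sizes and the SDs differ.

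**Worked example.** 50 and 100 patients, survivors' SD 2, deaths' SD 1. V(assumed) = 4/100 + 1/50 = 0.06. V(true) = 4/50 + 1/100 = 0.09. √(0.06/0.09) = 0.816; 1.96 × 0.816 = 1.600; the level is 11.0%.

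| Survivors/deaths | SD survivors : SD deaths | V(assumed) | V(true) | True level |
|---|---|---|---|---|
| 50/100 | 2 : 1 | 0.0600 | 0.0900 | 11.0% |
| 50/100 | 1.5 : 1 | 0.0425 | 0.0550 | 8.5% |
| 50/100 | 1.25 : 1 | 0.0356 | 0.0413 | 6.9% |
| 50/100 | 1 : 1 | 0.0300 | 0.0300 | 5.0% |
| 50/100 | 1 : 1.25 | 0.0413 | 0.0356 | 3.5% |
| 50/100 | 1 : 1.5 | 0.0550 | 0.0425 | 2.6% |
| 50/100 | 1 : 2 | 0.0900 | 0.0600 | 1.6% |
| 40/110 | 2 : 1 | 0.0614 | 0.1091 | 14.2% |
| 40/110 | 1 : 2 | 0.1091 | 0.0614 | 0.9% |

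Simulation of the exact t-test agrees to within about 0.2 percentage points. In the same settings Welch's test stayed between 4.8% and 5.1%.

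**Other sizes.** Over totals of 60, 100 and 200, and non-survivor shares from 50% to 80% (20,000 simulated data sets per cell), Student's test held 4.7% to 5.3% with equal SDs at every split. It held about 5% with equal sizes at every SD ratio from 0.5 to 2. Welch's test held 4.7% to 5.3% in every cell.

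**Does the normality test help or harm?** The two-stage rule (Shapiro–Wilk at 0.05, then Student's t or Mann–Whitney) was simulated with 4,000 data sets per cell.

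- Equal SDs, normal data: 4.4% to 5.7%. Gamma and lognormal data: 4.6% to 5.7%. The pre-test does no material damage.
- Normal data, 70% non-survivors: 8.1% to 10.2% when their SD is 0.67 of the survivors', and 2.0% to 2.7% when it is 1.5 times. Shapiro–Wilk on the pooled data still sent about 80% to 92% of data sets to Student's test, so it does not screen out unequal variances.

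**Price of Welch when it is not needed.** With 50 and 100 patients, equal SDs and a true difference of 0.5 SD (assumed), simulated power is 81.6% for Welch and 82.0% for Student.

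**The case against.** The strongest reply is that every driving figure is assumed. The plan gives no group sizes and no SDs, and nothing in it shows that spreads differ by outcome. That stands, and the point is therefore conditional. The 14.2% and 0.9% figures are corner cases, not estimates for this study.

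Four stronger readings are tempting, and the documents do not support them.

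- A reader might infer that unequal group sizes alone spoil the 5% level. They do not: with equal SDs the level holds at every split.
- A reader might blame the normality pre-test and ask for it to be dropped. With equal SDs the two-stage rule kept close to 5%. Its shortcoming here is only that it says nothing about variance.
- A reader might infer that noise variables enter the model at 8% to 14%. A variable wholly unrelated to mortality has the same distribution in both groups, hence the same SD, and keeps 5%. The distorted levels apply to variables with equal means but different spread by outcome.
- A reader might take it that these p-values decide model entry. Univariable analysis could equally mean univariable logistic regression, and clinical relevance is a separate route in.

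It is also fair to say that replacing Mann–Whitney with Welch's test on selectively logged values would only exchange one variable-by-variable choice for another. Mann–Whitney is not immune to unequal spread: it drifted to 6.8% to 7.6%, or 3.0% to 3.8%, in the 70:30 cells above. That does not make a wholesale replacement clearly better, since Welch's test was checked under unequal spread only on normal data.

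**Conclusion.** The point holds in a limited form and is minor. The plan names Student's t-test with no provision for unequal variances, in a comparison whose group sizes the design does not balance. Where a variable's SD also differs between groups, the 5% threshold does not mean 5%. For 50 survivors and 100 deaths with a 1.5-fold to 2-fold difference in SD, the true level is about 8.5% to 11% or about 1.6% to 2.6%, depending on which group is more variable. A ratio of 1.25 moves it to 6.9% or 3.5%. With equal SDs there is no error.

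This rests on reading the groups as survivors and non-survivors, on their sizes being unequal, and on spread differing for at least some variables. An effect on the logistic model is possible only under one reading of the entry rule.

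**What to change.** Wherever the plan uses Student's t-test, specify Welch's t-test (in SPSS, the row for equal variances not assumed) and report the mean difference with its 95% CI. The Shapiro–Wilk test and Mann–Whitney for skewed variables may stay.

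One further sentence could name the groups compared and say which univariable analysis governs model entry. It would settle whether this point reaches the model, but the Welch change does not depend on it.

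The cost is negligible. No new data are needed, and almost no power is lost when variances are equal. The document is written in the past tense and dated after the inclusion window, so p-values may already exist. In that case they are re-read from the same SPSS output, and any table entries that change are updated.

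### Model variables chosen by univariable significance or undefined clinical relevance, then retested in the same patients with no limit tied to events, tend to give false predictors, exaggerated odds ratios and overfitting

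*Combined protocol and SAP*

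**What the plan says.** The Statistical Analysis Plan section gives the purpose of the model: "Multivariable logistic regression analysis was used to identify independent predictors of mortality". The entry rule follows: "Variables with clinical relevance or statistical significance in univariable analysis were included in the model". The only significance level in the document is general: "A p-value < 0.05 was considered statistically significant".

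The candidate pool is described under Data Collection by type only: "Baseline demographic, clinical, laboratory, and resuscitation-related variables were collected from hospital electronic systems". There is no list or count of candidates, and no definition of clinical relevance.

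Selection and fitting use a single cohort: "This study is a retrospective observational cohort study conducted in a tertiary adult intensive care unit". The Study Population section gives a 17-month admission window but no sample size. The Outcome Measures section names 30-day mortality as primary and two further mortality endpoints as secondary. The plan does not say which of the three the regression uses. It describes no cap on model size, multiplicity control, shrinkage or internal validation.

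**The concern.** The rule has two routes into the model, and neither is fixed independently of the outcome.

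- **Univariable significance.** Each candidate is tested against death, the survivors of that test are refitted together, and they are tested again in the same patients. A variable that passed by chance carries its chance association into the second test. A real predictor tends to pass when its estimate happens to be high. Standard logistic regression output treats the chosen variables as if they had been given in advance, so its p-values and intervals do not reflect the selection.
- **Clinical relevance.** Choosing on clinical grounds is sound if the list is settled without sight of the outcome. Here the list is not given, and the criterion is joined by *or* to the data-driven one. A reader cannot tell which variables came in by which route.

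Identifying independent predictors is the regression's stated purpose. The list of predictors, the size of their odds ratios and the model's performance in other patients are all at stake.

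**Working it through.** The plan gives no figure to reproduce. The checks below rest on assumptions.

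**Inputs**
- From the document: significance level 0.05, selection and fitting in one cohort, no cap. Using 0.05 as the screening threshold is an inference, because no separate threshold is stated.
- Assumed: N = 150 (range 100–250), 65% mortality, and 40 uncorrelated candidates of which 5 are real, each with log odds ratio 0.4 per SD (odds ratio e^0.4 = 1.49).

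**Step 1: chance findings at the screen.** For k independent null candidates, P(at least one passes) = 1 − 0.95^k.
- k = 10: 40.1%
- k = 20: 64.2%
- k = 30: 78.5%
- k = 40: 87.1%

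The assumed case has 40 − 5 = 35 null candidates, so 35 × 0.05 = 1.75 are expected to pass, and P(at least one) = 1 − 0.95^35 = 83%.

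**Step 2: screen, refit and retest.** Simulation of the significance route: a t-test screen at 0.05, a logistic refit, p < 0.05 called an independent predictor, and performance measured in 20,000 new patients. The comparator is an unpenalised fixed list of seven variables, 4 real and 3 noise. Results at N = 150:

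| Quantity | Screen, then refit | Fixed list |
|---|---|---|
| False independent predictors per analysis | about 1.0 | 3 × 0.05 = 0.15 |
| Chance of at least one | 63–68% | about 15% (1 − 0.95^3 = 14%) |
| Inflation of log odds ratio, all reported real predictors | about 40% | 4–6% |
| Same, only those reaching significance | 47% | 43% |
| Calibration slope in new patients (ideal 1) | 0.47 | 0.68 |
| AUC, apparent and in new patients | 0.76 and 0.63 | 0.73 and 0.67 |

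Inflation of 40% turns a log odds ratio of 0.40 into 0.56, so a true odds ratio of 1.49 is reported on average as about e^0.56 = 1.75. Under the screen, inflation over all reported real predictors is about 66% at N = 100 and 17% at N = 250. For the fixed list it stays within about 0–9% over that range. Repeat runs differ by a few percentage points.

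**Step 3: sensitivity to the assumptions**
- Over 18 settings (N = 80, 150 or 300; 20, 30 or 40 candidates; correlation 0 or 0.3; mortality 61–63%), the chance of at least one false predictor was 26–85% and the calibration slope 0.25–0.78.
- N = 300 with 15 candidates: 31% chance of a false predictor, slope 0.80.
- N = 500 with 20 candidates: inflation only 3%, but still a 37% chance of a false predictor.
- N = 150 with candidates correlated at 0.2: the chance of a false predictor falls to 36%, but about 20 variables enter against about 52 survivors, or 52/20 = 2.6 survivors per variable.

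**Step 4: what a one-in-ten cap would allow.** At 65% mortality the smaller group is the survivors, 0.35 × N.
- N = 100: 35 survivors, 3 parameters
- N = 150: 52.5 survivors, 5 parameters
- N = 250: 87.5 survivors, 8 parameters

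The seven-variable comparator exceeds this cap at N = 100 and N = 150. It shows the effect of fixing the list, not the performance of the recommended model.

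**The case against.** **The size is assumed.** This stands. Sample size, deaths, candidates and effect sizes are all absent, and only the significance route was simulated. The flaw in the p-values and intervals follows from the rule itself. Its size does not, which is why the heading says *tend to*.

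**A fixed list does not cure everything.** This also stands. A reader might set the inflation of significant predictors under the screen against the inflation of all coefficients under a fixed list, and conclude that fixing the list removes nearly all of it. That comparison is not like for like. Among significant real predictors, inflation is similar (47% and 43%), because low power combined with a significance filter produces it either way. The gain appears when every coefficient is reported: about 40% against 4–6%. Some overfitting also remains with the fixed list (slope 0.68).

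**The screen discards U-shaped predictors.** A reader might infer this from the group comparisons of means or ranks. The text does not support it. A variable that fails the test can still enter as clinically relevant, and the document does not say that those comparisons are the univariable analysis it means.

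**The reported AUC will be too high.** The plan applies ROC analysis to severity scores, not to the fitted model. The AUC gap matters only if the model's own AUC is reported.

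**The variables were picked after the outcomes were seen.** Admissions ended on May 31, 2025, so six-month follow-up ended about November 30, 2025. The document is dated April 16, 2026 and written in the past tense. That means prior specification cannot be shown. It does not prove that the choice was made on the results, since an earlier plan may exist.

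**Conclusion.** The concern holds as a fault in a stated rule, not merely as missing detail. Selection on the outcome followed by retesting in the same patients, with no limit tied to the smaller outcome group, gives p-values and intervals that do not mean what they appear to mean. Nothing elsewhere in the document offsets this.

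Confidence is high on the principle and only illustrative on the size. Under the assumed 150 patients, 65% mortality and 40 uncorrelated candidates, about one declared predictor per analysis is false, and the odds ratios of real predictors are clearly overstated. With several hundred patients and a short candidate list, the inflation becomes small, though a false predictor remains a material possibility. The sponsor can place the study within this range once the sample size, deaths and number of candidates examined are stated.

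**What to change.** Replace the entry rule in the Statistical Analysis Plan with:

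> The 30-day mortality model contains a fixed list of predictors chosen from clinical knowledge and prior literature, not from their association with outcome in this cohort. The number of parameters, including any non-linear terms, is at most one tenth of the smaller of deaths and survivors; predictors are ranked in advance and the list is cut to meet this limit. All listed predictors are kept and all coefficients reported whatever their p-value. Univariable results are descriptive and do not decide inclusion.

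This wording also settles which endpoint the model serves. Penalised estimation is an optional addition.

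A list fixed now cannot be called prespecified, because follow-up has ended. If outcome associations in this cohort have already been examined, the report should say so and label the model exploratory.

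The cost is a change of wording and one rerun, with no new data. The model will hold fewer variables (about 5 parameters under the assumed 150 patients and 65% mortality) and probably show fewer significant predictors.
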